8.1.2 Somatic (non-inheritable) EGFR mutation testing

Where suitable tumour/cytology material is available, tumour DNA extraction and somatic mutational analysis should be carried out.

8.1.3 Reporting of EGFR mutation testing results

The *EGFR* mutation test result obtained from the patient's tumour will be sent to the investigator as per local practices and will be recorded in the study eCRF. The result will not be made available to any insurance company, the patient's employer, or the patient's family without the patient's specific consent.

9. HANDLING, STORAGE AND DESTRUCTION OF BIOLOGICALSAMPLES

Procedures for the handling and storage of samples will follow local lab requirements and practices. Sample processing should follow study site or central lab standard procedure in the context of applicable local regulation.

Study investigators will be encouraged to retain the residual DNA derived from tumour samples for possible future verification of results.

9.2 Withdrawal of informed consent for donated biological samples

Collection of mandatory tumour and blood (plasma) samples is an integral part of the study. If a subject withdraws consent to the use of any mandatory samples, the subject is withdrawn from further study participation and the samples will not be analysed.

If a subject withdraws consent to the use of blood (plasma) samples for molecular analysis at the nominated expert laboratory, residual blood (plasma) samples (and any derivatives thereof) if remaining after analysis, will be destroyed.

If a subject withdraws consent to the use of optional tumour samples for exploratory biomarker analysis, the subject can continue in the study. If a subject withdraws consent to the use of optional tumour samples during the study and the sample is held at a central facility (nominated by AstraZeneca), then the tumour blocks will be repatriated, slides and any residual material or derivatives of the sample will be destroyed.

If tumour (mandatory or optional) or blood (plasma) samples have already been analysed before withdrawal of consent, AstraZeneca is not obliged to destroy the results of this research.

10. SAFETY REPORTING

Due to the non-interventional character of this study, no pro-active safety data collection should take place. Only spontaneously mentioned safety events should be reported as required by the post-marketing pharmacovigilance regulations.

11. ETHICAL CONDUCT OF THE NON-INTERVENTIONAL STUDY

The Non-Interventional Study will be performed in accordance with ethical principles that are consistent with the Declaration of Helsinki, ICH GCPs and the applicable legislation on Non-Interventional Studies.

The Investigator will perform the NIS in accordance with the regulations and guidelines governing medical practice and ethics in the country of the NIS and in accordance with currently acceptable techniques and know-how.

12. STATISTICAL METHODS AND SAMPLE SIZE DETERMINATION

12.1 Description of outcome variables in relation to objectives and hypotheses

No formal statistical hypothesis tests will be made in this study.

The relationship between the objectives and outcome variables is described in the table below.

Objectives	Outcome variables	
Primary objectives		
To determine the level of concordance between EGFR mutation status obtained via tissue/ cytology and blood (plasma) based testing.	Concordance rate, sensitivity, specificity, positive and negative predictive values between sample types.	
Secondary objectives		
- To determine the EGFR mutation frequency (including mutation subtypes) in patients with advanced NSCLC (aNSCLC) of adenocarcinoma and non- adenocarcinoma histologies.	EGFR mutation frequency overall and by adenocarcinoma and non-adenocarcinoma histologies and by country/region.	
- To describe first line therapy choice following EGFR mutation testing.	% first line treatment choices by mutation status and by country/region and mutation subtype.	
 To describe second line therapy choice following discontinuation of first line treatment for patients confirmed as EGFR mutation positive via tissue/cytology. 	% patients on 2 nd line treatment, treatment sequence, % second line treatment choices by country/region and mutation subtype for EGFR mutation positive for tumour.	
 To summarise EGFR mutation testing practices in terms of methods, sample types, success rate, mutation detection rate, testing turnaround time and reasons 	EGFR mutation test method, sample type, success rate, mutation detection rate, testing turnaround time and reasons for testing not being performed summarised overall and by	

Table 4: Study objectives and outcome variables

for not testing.

- To determine the correlation between *EGFR* mutation status from tumour and demographic data and disease status.
- To determine the correlation between EGFR mutation status derived from plasma (blood) and demographic data and disease status

country/region.

Correlation of mutation status from tumour with demographic characteristics and disease status data.

Correlation of mutation status from plasma (blood) with demographic characteristics and disease status data.

13. DESCRIPTION OF ANALYSIS SETS

13.1 Enrolled Population

The Enrolled Population consists of all patients who sign an informed consent.

13.2 Evaluable Population

The Evaluable Population consists of all enrolled patients with all non-missing or unknown:

- Tumour sample *EGFR* mutation test status.
- Tumour sample *EGFR* mutation test sub-type.
- Plasma *EGFR* mutation test status.
- Plasma *EGFR* mutation test sub-type.

Unless otherwise specified all summaries will be based on the Evaluable Population.

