7.2 Secondary variables

The following data will be collected in order to fulfil the secondary objectives of the study:

Patient demographics	• Gender		
	• Age		
	• Race		
	EthnicityWHO Performance status		
	• Smoking status:		
	• Intensity (cigarettes per day)		
	o Duration (years)		
	• Time since cessation (years)		
	• Disease status:		
	 Date of first diagnosis 		
	 Histological type 		
	• TNM (AJCC) disease stage		
	(Edition 7)		
	• Number of organs with		
	metastasis		
	• Location of		
	metastasis/metastases		
1 st -line treatment decision after testing	• Name of treatment		
	• Treatment start date		
	• Reason for treatment choice (including		
and 1. () 1. () ()	Clinical Trial enrolment)		
2 nd -line treatment decision (for patients	• Name of treatment		
confirmed as EGFR mutation-positive via	• Treatment start date		
tissue/cytology)	• Reason for treatment choice (including		
	Clinical Trial enrolment)		
EGFR mutation testing endpoints	• Test result		
	• Overall mutation result (positive		
	negative, unknown)*		
	• Mutation subtype		
	 Testing methodology Sample time and envilopility 		
	• Sample type and availability		
	 Testing turnaround time Basson(a) for testing not being 		
	 Reason(s) for testing not being performed 		
Footnote:	performed		

Footnote:

Smoking is a multi-dimensional phenomenon with many characteristics, such as intensity (in cigarettes per day), duration (in years) and time since cessation (in years). In this study, every patient should report the all information list above to determine the smoking status.

- Deletion, substitution, and/or insertion mutations of tyrosine kinase domain of the *EGFR* gene will be identified and recorded in the CRF. Methods used for measuring *EGFR* mutation status should also be recorded.

*EGFR mutation status will be recorded for each patient as:

- Positive: *EGFR* mutation detected (one or more individual mutations)
- Negative: EGFR mutation not detected
- Unknown: *EGFR* mutation status not determined as *EGFR* mutation positive or *EGFR* mutation negative

It is accepted that mutation assays (methods and individual mutation assays) may differ between labs and institutions. Thus a patient can be positive or negative depending on the method used. As a minimum, laboratories should assess the common *EGFR* mutations: Exon 19 deletions, and Exon 21 L858R point mutations.

Mutation subtypes will also be recorded:

- Exon 18:
 - o G719C/S/A
 - 0 other
- Exon 19:
 - o deletions
 - o other

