14.1 Primary Objective

The concordance rate, sensitivity, specificity, positive and negative predictive values and their exact 2-sided 95% confidence interval for comparing mutation status between tumour and plasma samples will be calculated for evaluable population for Europe and Japan.

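### As written, the Evaluable Population requires a mutation sub-type from both samples, so mutation-negative patients drop out, contrary to the planned primary analysis

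*Protocol*

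**What the plan says.** Section 13.2 of the Protocol opens its definition with "The Evaluable Population consists of all enrolled patients with all non-missing or unknown" and lists four items: tumour status, "Tumour sample *EGFR* mutation test sub-type", plasma status and "Plasma *EGFR* mutation test sub-type". No condition restricts the two sub-type items to samples in which a mutation was found. The section then makes this the default set: "Unless otherwise specified all summaries will be based on the Evaluable Population".

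Section 14.1 uses the same set for the primary objective: concordance, sensitivity, specificity, PPV and NPV "will be calculated for evaluable population for Europe and Japan".

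Section 7.2 defines the result categories, including "Negative: EGFR mutation not detected". Its sub-type list, by exon 18 to 21, contains only actual mutations, with an 'other' entry under each exon. It has no entry for none or not applicable.

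Section 15 sizes the study on 100 tumour-positive patients, an assumed sensitivity of 50% and a 95% CI of 40-60%.

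**The concern.** The primary measures compare two binary statuses, and sub-type enters none of them. Section 13.2 nevertheless makes sub-type a condition of entry, in a form that a negative sample cannot meet. A patient who is negative in either sample fails at least one of the four items. Specificity and NPV need exactly those patients, and so does any sensitivity below 100%.

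The stem adds to the difficulty. 'Non-missing or unknown' presumably means neither missing nor unknown, but it can also be read as admitting unknown results, and an unknown status has no cell in the two-by-two table.

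At stake is the membership of the primary analysis set and, by default, of every other summary. Whoever programs the analysis must replace the written rule with one the protocol does not state, and the possible replacements do not all give the same patients.

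**Working it through.** **Inputs.** From section 15: 1000 European and 300 Japanese patients, mutation frequency 10% and 30%, sensitivity 50%. From section 13.2: the four entry items. The counts below assume that every enrolled patient has a definite result in both samples.

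**The plan's own figure.** With n = 100 and p = 0.5, the Wald interval is 0.5 ± 1.96 × √(0.25/100) = 40.2-59.8%; the exact interval is 39.8-60.2%. The stated 40-60% reproduces. In Europe 1000 × 10% = 100 positives, as stated. In Japan 300 × 30% = 90, not the stated 100. That is a separate matter; 90 is used here.

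**Table the plan needs.**

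| | Tumour+/plasma+ | Tumour+/plasma− | Tumour-negative |
|---|---|---|---|
| Europe | 100 × 50% = 50 | 50 | 900 |
| Japan | 90 × 50% = 45 | 45 | 210 |

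**Reading 1: the rule as written.** The stem is taken as neither missing nor unknown, and an absent sub-type as missing.
- Tumour+/plasma− fails on plasma sub-type. Tumour−/plasma+ fails on tumour sub-type. Double negatives fail on both.
- Remaining: 50/1000 = 5% in Europe and 45/300 = 15% in Japan.
- Sensitivity is 50/50 = 100% (exact 95% CI 92.9-100%) in Europe and 45/45 = 100% (92.1-100%) in Japan.
- Concordance and PPV are also 100% by construction. Specificity and NPV are 0/0.

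**Reading 2: sub-type required only of positive samples.** Let u be the share of plasma positives with no recorded sub-type. The protocol gives no value, so u is assumed. True and false positives are lost; false negatives and true negatives stay.

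Observed sensitivity = s(1−u) / [s(1−u) + (1−s)], with s = 0.5:
- u = 0: 50%, no bias
- u = 5%: 0.475/0.975 = 48.7%
- u = 10%: 0.45/0.95 = 47.4%
- u = 20%: 0.40/0.90 = 44.4%

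Specificity moves up slightly. With an assumed true value of 97% (Europe: 873 true negatives, 27 false positives), it is 873/[873 + 27(1−u)] = 97.1%, 97.3% and 97.6% at u = 5%, 10% and 20%.

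Now let a share m of tumour positives lack a sub-type, unrelated to the plasma result. Both cells of the sensitivity row shrink by (1−m), which cancels, so sensitivity stays at 50% and only precision is lost: at m = 10%, 100 positives become 90. Concordance shifts a little because positives become rarer in the set: with 97% specificity, from (50 + 873)/1000 = 92.3% to (45 + 873)/990 = 92.7%.

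**Reading 3: the stem admits unknown results.** Patients with an unknown status enter the set, and the two-by-two table has no place for them.

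**The case against.** The strongest reply is that nobody would apply the rule literally, because the protocol excludes that reading. Section 14.1 asks for specificity and NPV in this set, section 14.2 fits logistic models of mutation-positive against mutation-negative patients in it, and section 15 plans for 50% sensitivity. On this view a negative sample's sub-type is not applicable rather than missing, and such coding is ordinary SAP work. The argument stands as evidence of intent. A reader might infer from section 13.2 that the study will report 100% sensitivity and no specificity; the documents do not support that. The written rule still says something else, and it is a stated condition rather than a detail left open.

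A reader might also infer that the milder reading biases sensitivity as a matter of course. It does not. The bias is zero if every plasma positive has a recorded sub-type. Section 7.2 requires detected mutations to be recorded and offers 'other' entries, and plasma goes to nominated laboratories (section 2.2, Table 2), where incomplete reporting is less likely. At the assumed 5% or 10% the shift is 1.3 or 2.6 points, small against a 40-60% interval, and it does not flatter plasma.

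A third inference is that leaving out failed plasma tests is an error that overstates plasma performance. Accuracy among valid paired results is a conventional target, and section 7.2 defines failure and success rates separately. Counting failures as not detected answers a different question: at an assumed failure rate of 5% or 10%, 50% among successful tests becomes 0.5 × 0.95 = 47.5% or 0.5 × 0.90 = 45% of all tumour-positive patients sampled. That is a choice of estimand.

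**Conclusion.** The point holds as a contradiction within the protocol. Section 13.2 as worded removes every patient with a negative result in either sample, leaving about 50 of 1000 and 45 of 300, while sections 14.1, 14.2 and 15 depend on those patients. This conclusion needs only the section 15 inputs, definite results in both samples, and the fact that a negative result carries no sub-type.

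Under the milder reading, what is certain is that the rule makes entry depend on information no primary measure uses. The downward bias in sensitivity is conditional on an unstated rate of missing plasma sub-types. Missing tumour sub-types cost precision for sensitivity but do not bias it, provided they are unrelated to the plasma result.

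Because the wording fixes the primary analysis set, it should be corrected even though the intent can be inferred.

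**What to change.** - Define the primary Evaluable Population as enrolled patients with a positive or negative *EGFR* status, neither missing nor unknown, from both the tumour and the plasma sample. This also replaces the unclear stem.
- Require a known sub-type only for sub-type summaries among positive samples.

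This restores the table section 15 planned: 50 of 100 in Europe (exact 95% CI 39.8-60.2%) and 45 of 90 in Japan (39.3-60.7%), given definite results throughout. The cost is a change of wording, with no new data and no change in sample size.

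Optionally, add one supportive table in which tumour-positive patients with an unknown plasma result count as not detected. It would give a somewhat lower sensitivity and would bear on whether plasma is a suitable sample type, but it is an addition and not the correction of an error.

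### The Evaluable Population in section 13.2 asks every patient for a mutation sub-type from both samples, which a negative sample cannot supply; the wording contradicts the analyses planned on that set

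*Protocol*

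**What the plan says.** Protocol section 13.2 defines the primary analysis set: "The Evaluable Population consists of all enrolled patients with all non-missing or unknown", followed by four items. Two are the tumour and plasma mutation status. The other two are "Tumour sample *EGFR* mutation test sub-type" and "Plasma *EGFR* mutation test sub-type". Neither sub-type item is limited to positive samples. The same section makes this set the default for all summaries.

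Section 7.2 defines the status categories, among them "Negative: EGFR mutation not detected". It then states "Mutation subtypes will also be recorded" and lists exon 18, 19, 20 and 21 mutations, each exon with an entry for other variants. The list has no entry for none, wild-type or not applicable.

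Section 14.1 plans concordance, sensitivity, specificity and both predictive values, with exact intervals, "for comparing mutation status between tumour and plasma samples will be calculated for evaluable population for Europe and Japan". Section 14.2 uses the same set for mutation frequency and for logistic models of positive versus negative tumour status. Section 7.1 names both status and sub-type, from both samples, as the primary variable.

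**The concern.** The definition and the analyses built on it do not fit together. If all four items are compulsory, a patient with a negative result on either sample has an empty sub-type field and drops out. That removes every tumour-negative patient, who is needed for specificity and negative predictive value. It also removes every tumour-positive, plasma-negative patient, and these are the missed cases that sensitivity has to count.

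The lead-in adds to the difficulty. Read word for word, it could admit unknown values; the sensible meaning is neither missing nor unknown. The wording does not bring negatives back in either case, because the sub-type of a negative sample is absent rather than unknown. Negatives stay only under a coding rule that the protocol does not state.

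A milder problem remains under the sensible reading, in which sub-type is required only where a sample is positive. A patient whose status is known to be positive but whose sub-type was not reported is then excluded from a comparison of status. Only positives can be lost this way, and the number of positives is what drove the sample size.

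**Working it through.** **Inputs.** From section 15: Europe 1000 patients with 10% mutation frequency; Japan 300 patients with 30%; sensitivity 50%. Plasma specificity is not given. It is assumed to be 100%, with 90% as the other end of the range. No failed tests are assumed.

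**The plan's own figure.** Section 15 states a 95% interval of 40-60% for 50% sensitivity in 100 positives. The exact (Clopper-Pearson) interval for 50/100 is 39.8-60.2%, so the figure reproduces. For Europe, 1000 × 0.10 = 100 positives, as stated. For Japan, 300 × 0.30 = 90, not the stated 100. That is a separate matter, and 90 is used below.

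**Intended set (status known on both samples).**
- Europe: 50 positive on both, 50 tumour-positive and plasma-negative, 900 tumour-negative. Sensitivity 50/100 = 50%. Concordance (50 + 900)/1000 = 95.0% at 100% specificity, or (50 + 810)/1000 = 86.0% at 90%.
- Japan: 45, 45 and 210. Sensitivity 45/90 = 50% (exact interval 39.3-60.7%). Concordance (45 + 210)/300 = 85.0% at 100% specificity, or (45 + 189)/300 = 78.0% at 90%.

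**Set as worded (sub-type required from both samples).** Number kept = N × frequency × sensitivity.
- Europe: 1000 × 0.10 × 0.50 = 50, or 5% of patients. Sensitivity 50/50 = 100% (exact interval 92.9-100%).
- Japan: 300 × 0.30 × 0.50 = 45, or 15% of patients. Sensitivity 45/45 = 100% (exact interval 92.1-100%).
- In both regions status concordance and positive predictive value are 100%, specificity and negative predictive value are 0/0, and tumour mutation frequency is 100%. The models of tumour status have no negative outcomes and cannot be fitted.

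The 100% values do not depend on the assumed sensitivity or specificity. The numbers kept do not depend on specificity, because a plasma false positive is tumour-negative and has no tumour sub-type.

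**Set with sub-type required only of positive samples.** The share of positives without a reported sub-type is not in the protocol; 5, 10 and 20% are assumed.

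| Share without sub-type | Sensitivity, loss among plasma-positives (Europe) | Tumour frequency, loss among tumour-positives (Europe) |
|---|---|---|
| 0% | 50/100 = 50% | 100/1000 = 10% |
| 5% | 47.5/97.5 = 48.7% | 95/995 = 9.5% |
| 10% | 45/95 = 47.4% | 90/990 = 9.1% |
| 20% | 40/90 = 44.4% | 80/980 = 8.2% |

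The sensitivity column also holds for Japan, since the ratios are the same. For frequency in Japan at 10% loss, (90 − 9)/(300 − 9) = 27.8% instead of 30%.

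Missing tumour sub-type lowers the frequency. It shifts sensitivity only if it is related to the plasma result. If unrelated, it removes plasma-positive and plasma-negative patients in proportion and costs precision only.

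**The case against.** The strongest reply is that nobody would apply section 13.2 literally. Specificity and negative predictive value are planned on this set, frequency and positive-versus-negative models are run on it, and section 15 assumes 50% sensitivity, which requires plasma-negative patients. A set of double-positives would fail at the first table, and a negative sample's sub-type is naturally read as not applicable rather than missing. The lead-in also needs repair before it can be read at all, so strict literalism about the sub-type items alone would be selective. This stands as an argument about intent. A reader might infer that the study will report 100% sensitivity and concordance; the protocol does not support that. The argument also concedes that the definition contradicts the analyses and that the reader must supply an unwritten rule.

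A second reply is that sub-type belongs in the set because section 7.1 makes it part of the primary variable. The premise is right and the fix must respect it, but the section 14.1 measures compare status only.

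A third reply concerns the milder problem. Section 7.2 provides an entry for other variants within each listed exon, and plasma is tested at nominated laboratories, so few positives may lack a sub-type. This also stands. The 5-20% range is an assumption, and the resulting sensitivities stay inside the planned 40-60% interval. A reader might infer that sensitivity will be materially biased; the documents do not show that. Losses are nonetheless plausible on the tumour side, where testing follows local practice, earlier results are accepted, and section 7.2 allows assays to differ between laboratories.

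Finally, the analysis plan may clarify the coding. It is not at hand, but this is not a detail left open: the protocol itself fixes the primary analysis set, so an analysis plan must either inherit the wording or depart from it.

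**Conclusion.** The point holds as a defect in the stated definition of the primary analysis set. Followed as written, the rule retains about 5% of European and 15% of Japanese patients and makes the primary estimates uninformative. This is a consequence of the text and not a forecast, because sections 12.1, 14.1, 14.2 and 15 all presuppose negatives. Confidence in the wording defect is high.

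The remaining effect under the sensible reading runs in one direction and is modest. At an assumed 5-20% loss, sensitivity falls by 1.3 to 5.6 percentage points through missing plasma sub-type, and European frequency by 0.5 to 1.8 points through missing tumour sub-type. The real rate is unknown and could be close to zero. The change is still needed because the set governs every primary estimate and is the default elsewhere.

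**What to change.** Replace the definition in section 13.2 with: the Evaluable Population consists of enrolled patients whose tumour status and plasma status are each positive or negative. This removes the two sub-type items and the garbled lead-in together.

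Because section 7.1 makes sub-type part of the primary variable, add a separate sub-type subset (status positive and sub-type known) for the sub-type analyses, and carry both definitions into the analysis plan. Adding only a qualifier that sub-type is needed where the sample is positive would remove the contradiction, but would still drop positives from the status comparison.

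The cost is a short text change and no new data. Sub-type tables will have a slightly different denominator from status tables, which should be stated in the tables.
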